## 5. SAMPLE AND RECRUITMENT

### 5.1. Eligibility Criteria

#### 5.1.1. Inclusion criteria

- **All**
  - Self-reported current cigarette smoker
  - Carbon Monoxide (CO) reading  $\geq 5$  ppb
  - Intends to quit smoking / undertake a smoking quit attempt within 3 months.
  - No prior history of cancer
  - Able to provide informed consent
- **Lung Health Check attendees**
  - Aged  $\geq 55$  years
  - $PLCO_{M2012}$  score  $\geq 1.51\%$  (or eligible for screening if alternative risk model is used)
- **MFT-CURE attendees**
  - Aged  $\geq 40$  years

#### 5.1.2. Exclusion criteria

- **All**
  - Never or former smoker (has not smoked within the last 2 weeks)
  - Carbon Monoxide (CO) reading  $< 5$  ppb
  - Prior history of cancer
- **Lung Health Check attendees**
  - Aged  $< 55$  years
- **MFT-CURE attendees**
  - Aged  $< 40$  years

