#### 3.3. Data analysis

The clinical cohort will be stratified according to smoking status at timepoint 3 into a Quit Cohort (stopped smoking for 3 months or more at the time of sample collection) and a Smoking Cohort (smoked within 3 months of sample collection). Analysis of laboratory data will be stratified over time (baseline compared to timepoint three) and according to final cohort categorisation.

Machine learning algorithms will be developed to integrate across all of the features of the multi-omics analysis of normal tissues, to identify the combinations of parameters that contribute most to cancer risk. We will integrate salient features of the dynamics of tissue perturbation by tumour promoters including the clonal structure of tissues, protein and gene expression patterns, and differences in the pattern of infiltration of immune cell populations. In order to understand the association between these features and carcinogenesis. We will study whether they can be used to discriminate between groups of samples before or after intervention. We propose an analysis that is organized in logical steps with increasing degrees of complexity.

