**5.4.3. Timepoint 3 (TP3)**

Samples collected at TP3 include the following

- Buccal swab
- Mouthwash sample
- Breath carbon monoxide measurement
- Study questionnaire
- Nasal swab (optional)
- Nasal brush (optional)
- Blood sample (optional) - 50mL volume maximum

TP3 participants will be classified as either **a former smoker** (last cigarette over three months ago i.e. a last cigarette 3 months plus 1 day ago = former smoker) **or current smoker** (smoked a cigarette within the last three months).

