**6.8. Expenses and Benefits**

**PROMINENT Smoking Cessation Study**

We will offer participants who donate at least two sets of samples a £20 shopping voucher as a token of appreciation for their participation in the study. Those who attend the third visit will receive an additional £20 shopping voucher. We will also offer to pay carpark tickets or reasonable travel expenses for participants.

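### The breath CO entry threshold is printed in ppb and so hardly screens anyone, and the protocol gives the CO measured at TP3 no role in deciding who counts as having quit

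*Protocol*

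**What the plan says.** **Entry.** Section 5.1.1 requires a "Carbon Monoxide (CO) reading $\geq 5$ ppb" and section 5.1.2 excludes a "Carbon Monoxide (CO) reading $< 5$ ppb". The two lists agree with each other, and no other section gives a CO threshold in any unit. The remaining smoking criteria at entry rest on the participant's account: "Self-reported current cigarette smoker" in section 5.1.1, and the exclusion "Never or former smoker (has not smoked within the last 2 weeks") in section 5.1.2.

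**Follow-up classification.** Section 3.3 divides participants by their status at TP3. One group is the "Quit Cohort (stopped smoking for 3 months or more at the time of sample collection"). The other, for anyone whose last cigarette was more recent, is the "Smoking Cohort (smoked within 3 months of sample collection"). Section 5.4.3 uses the same basis and gives the example "a last cigarette 3 months plus 1 day ago = former smoker". Sections 3.2 and 5.4.2 obtain smoking status by questionnaire and telephone call.

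**CO at follow-up.** Sections 5.4.1, 5.4.3 and 5.4.4 and the schedule in Appendix 1 list a breath CO measurement at TP1, TP3 and TP4. Eligibility at baseline is the only use that the protocol states for it.

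**The concern.** Section 5.2.1 makes paired samples from smokers who go on to quit the primary aim. The comparison therefore depends on two labels being right: smoking at TP1 and abstinent at TP3.

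The TP1 label is meant to have one objective support, and as printed that support is set so low that it does almost no work. Someone who last smoked 13 days ago is not caught by the two-week exclusion. If that person also calls themselves a current smoker, only the CO criterion could stop them.

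The TP3 label has no stated objective support, although the measurement is taken at the same visit as the samples. Followed literally, the protocol keeps in the Quit Cohort a participant who reports abstinence but has a smoking-level CO reading on the day of sampling. Such pairs pull the estimated change after cessation towards zero. They also mislabel the group used for the e-cigarette comparison in section 2.1.1.

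These are two separate defects. Correcting the unit at entry does nothing to check quitting at TP3.

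**Working it through.** **1. The plan's own figure.** Section 5.2.1 gives a 20% quit rate, a minimum of 50 pairs and a maximum of 250 recruits. 50 / 0.20 = 250, so the figure reproduces. It has no margin: 250 × 0.20 = 50 is the expected number of quitters, and with a true rate of exactly 20% the binomial chance of reaching at least 50 is 0.53, before any loss to follow-up. The CO unit does not enter this calculation.

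**2. The entry threshold.** 5 ppb / 1000 = 0.005 ppm. The protocol does not describe the meter, so its resolution is an assumption:

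| Assumed smallest non-zero display | In ppb | Multiple of the printed threshold |
|---|---|---|
| 1 ppm | 1000 | 1000 / 5 = 200 |
| 0.1 ppm | 100 | 100 / 5 = 20 |

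In either case every non-zero reading meets the inclusion criterion, and only a displayed zero is excluded. If staff have instead applied the number 5 to a display in ppm, the working cut-off is 5000 ppb, which is 1000 times the printed one. With whole-ppm readings the two versions disagree for 1, 2, 3 and 4 ppm: the text admits these people and the practice turns them away.

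**3. The TP3 classification.** Reading sections 3.2, 3.3, 5.4.2 and 5.4.3 together:

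- Status is defined by time since the last cigarette.
- That time comes from the participant, by telephone or questionnaire.
- CO is listed at TP3 without a cut-off.
- No rule covers a reading that conflicts with the reported date.

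**4. Illustrative size.** The documents give no misreporting rate. Let m be the assumed share of classified quitters who still smoke, and suppose that they show no molecular change. The observed mean paired change is then (1 − m) times the true change. With the spread of the paired changes held fixed, the number of pairs needed for the same power rises by 1/(1 − m)². This factor restores power, not precision.

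| m (assumed) | True quitters among 50 | Mean change, share of true | Pairs for same power | Recruits for 50 true quitters, 50 / (0.20 × (1 − m)) |
|---|---|---|---|---|
| 0 | 50 | 1.0 | 1.00 × | 250 |
| 0.10 | 45 | 0.9 | 1.23 × | 278 |
| 0.20 | 40 | 0.8 | 1.56 × | 313 |

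**The case against.** The unit may be a clerical slip with no consequence. If the meters show ppm and staff apply 5, no participant has been wrongly enrolled. That is possible, and the documents show no actual harm to the baseline sample. But the printed criteria and the practice would then disagree, and section 6.6 requires deviations to be documented and reported, so the text still needs correcting.

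Only the protocol is at hand, and an SAP could say how follow-up CO is handled. For this reason the point is limited to what the protocol states. The protocol does, however, fix cohort membership itself, with no CO condition.

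CO detects only recent smoking and cannot confirm three months of abstinence. This is correct. Someone who smoked some weeks before TP3 would pass, so the check recovers only part of any dilution. It does identify the participant who is smoking around the time of sampling.

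A reader might also infer four stronger things that the documents do not support:

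- **That the criterion excludes nobody.** A displayed zero is still below 5 ppb and is still excluded. The wider claim needs meter and background figures that are not given.
- **That follow-up CO is never used.** The protocol states no use, which is a narrower finding.
- **That unused TP4 readings weaken Quit Cohort membership.** Membership is fixed at TP3, and TP4 is offered only to those already classed as former smokers.
- **That the vouchers reward false reports of quitting.** Section 6.8 says "Those who attend the third visit will receive an additional £20 shopping voucher", and Appendix 1 labels TP4 as Visit 3, so the payment does reach only reported quitters. But it pays for attending a further sampling visit, and nothing shows that participants know of the link when they report their status.

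**Conclusion.** Both parts hold. The CO threshold as printed, 0.005 ppm, hardly separates smokers from abstainers. This rests on the assumption that the meters display whole ppm, or at any rate steps well above 0.005 ppm. The unit is probably an error, but the documents do not confirm which unit was meant.

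Separately, Quit Cohort membership is defined by reported time since the last cigarette, and the protocol gives the CO taken at the same visit no role.

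The size of the effect is not known. The figures of 0.9 to 0.8 of the true change depend on an assumed 10–20% misreporting rate and on no change in misreporters. They should not be read as an estimate of bias in this study, nor as the amount that a CO check would recover. The study is exploratory and states no power or effect size, so the case for change rests on correct labels and on data already being collected.

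**What to change.** 1. **Sections 5.1.1 and 5.1.2.** Confirm the intended unit and the cut-off that staff have applied, correct both lists, and check enrolled participants' recorded TP1 readings against the corrected criterion.
2. **Sections 3.3 and 5.4.3.** For the main analysis, define the Quit Cohort as reported abstinence of more than three months together with a TP3 CO below the corrected cut-off. Report discordant cases (abstinence reported, CO at or above the cut-off) separately, and repeat the contrast on self-report alone as a sensitivity analysis. A low reading in the Smoking Cohort is not discordant, since that cohort includes people who stopped less than three months ago.
3. **Section 5.4.4.** Use TP4 CO only to check continued abstinence at TP4, because it cannot change TP3 membership. State whether the TP4 invitation follows reported status or the CO-checked status.

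**Cost.** CO is already collected at all three sampling visits, so no new measurement is needed. The work is a wording change, a record check and a little more analysis. Any discordant pair leaves the Quit Cohort, whose expected size of 250 × 20% = 50 only just equals the stated minimum, so the protocol should acknowledge that the CO-checked group may fall below 50.

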### 5.2. Sampling

#### 5.2.1. Size of sample

The study is exploratory; the primary aim is to analyse paired sequential samples from current smokers who successfully quit smoking. Based on our data, approximately 20% of current smokers are able to quit therefore to ensure a minimum of 50 paired samples, up to 250 current smokers will be recruited at baseline. We also aim to recruit paired samples from participants who are current smokers at baseline and at timepoint 3.

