### 1.2. Manchester CURE (stop smoking) Project

Manchester has implemented a vanguard programme of hospital-based tobacco-dependency treatment services. The Manchester CURE project (*Conversation-Understand-Replace-Experts/Evidence-base*) has translated the published evidence base of the effectiveness of hospital-based tobacco dependency treatment (the Ottawa Model of Smoking Cessation and randomised controlled trial data) into a resilient, sustainable, and scalable real-world clinical service model (9-12). The CURE team approach every patient that smokes and offers a review of pharmacotherapy, specialist behaviour change support, and motivational interviewing. A key part of this specialist consultation is also offering and agreeing a treatment and support plan after discharge. The CURE team offer ongoing medications and support following discharge, through regular outpatient consultations (face to face or telephone) for 12 weeks or referral to community services for ongoing support. In a pilot of the CURE project the self-reported 12 week quit rate for current smokers was 22% (13). The CURE project has expanded its reach beyond the inpatient pathway to provide outpatient services and tobacco dependency treatment within the Greater Manchester Lung Health Check Programme. The same core principles are maintained within these programmes which include opt-out referral with immediate on the day specialist assessment to commence treatment and agree a further support package beyond the initial assessment. The clinical team will ask current smokers who wish to quit and are eligible for screening whether they would be interested taking part in the study. Those who express an interest will discuss the study with a member of the research team.

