### **5.3.3. Consent**

A written participant information sheet (PIS) will be provided. This will give information about the purpose of the study, what participation entails and will highlight the benefits and risks of participation. It will be clearly stated that taking part is voluntary and whether they participate or not this will not impact the medical care they receive. The study will also be explained verbally by a member of the research team. Participants will be given adequate time to review the information and have the opportunity to ask any questions they may have about the study.

Fully informed written consent is required prior to participation in the study. This will take place on the day of the study visit and will involve the participant signing a paper consent form. Consent will be taken by an appropriately trained member of the research team, who will also sign the consent form and give the participant a copy to take home. Participants are free to withdraw from the study at any time, without needing to give a reason. If a participant would like to leave the study the research team will ask for all data and samples collected up to the time of withdrawal to be kept; however, participants have the right to have data removed from the research database and samples collected as part of the study destroyed.

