## PROMINENT Smoking Cessation Study

**5.4.1. Timepoint 1 (TP1)**

Samples collected at baseline include the following

- Buccal swab
- Mouthwash sample
- Breath carbon monoxide measurement
- Personal data collection form
- Study questionnaire
- Nasal swab (optional)
- Nasal brush (optional)
- Blood sample (optional) – 50mL volume maximum

If it is not possible to take the nasal sample (brush or swab) for whatever reason the individual may continue in the study. If the buccal sample is not collected, then the individual will be withdrawn from the study.

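### Section 5.2.1 presents 50 quit pairs as an ensured minimum, but 50 is the expected number at maximum recruitment, before any loss, and the lower planned size of 150 gives an expected 30

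*Protocol*

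**What the plan says.** Section 5.2.1 calls the study exploratory and makes paired samples from smokers who succeed in quitting its primary aim. It then gives the protocol's only justification of size. The quit rate is "approximately 20% of current smokers are able to quit", attributed to the team's own data, and the conclusion is "therefore to ensure a minimum of 50 paired samples, up to 250 current smokers will be recruited at baseline". The Study Summary gives the planned size differently, as 150 to 250.

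The only other quit rate in the protocol is in section 1.2: "In a pilot of the CURE project the self-reported 12 week quit rate for current smokers was 22"%.

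Section 3.3 defines the Quit Cohort as those who have "stopped smoking for 3 months or more at the time of sample collection", judged at timepoint 3 (TP3). A quit pair therefore needs a baseline sample, at least three months of abstinence and a second sample. Section 5.3.3 says "Participants are free to withdraw from the study at any time, without needing to give a reason". Section 5.2.1 makes no allowance for withdrawal, loss to follow-up or a missing TP3 sample.

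Sections 5.4.1 and 5.4.3 make nasal swabs and brushes optional. Section 5.4.1 adds: "If it is not possible to take the nasal sample (brush or swab) for whatever reason the individual may continue in the study". A participant without a baseline buccal sample is withdrawn.

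**The concern.** A recruitment target obtained by dividing the number wanted by the expected rate gives the number wanted on average. About half the time the count falls short, even if the rate is exactly right and every quitter returns. Section 5.2.1 describes that average as something the design ensures. It also ties it to a ceiling on recruitment, while the Study Summary allows a total as low as 150.

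The 50 pairs carry the before-and-after comparison that section 5.2.1 names as the primary aim. The same quitters are divided again by e-cigarette use for the second primary objective in section 2.1.1. Anyone judging whether the cohort is large enough for those comparisons is told that 50 is secured, when it is the middle of a wide range.

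**Working it through.** **Inputs.** From section 5.2.1: quit rate p = 0.20, target 50, maximum n = 250. From the Study Summary: lower size n = 150. From section 1.2: p = 0.22, self-reported at 12 weeks. The protocol states no loss rate, so the values of d below are assumptions that show the range.

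**Step 1: reproduce the plan's figure.** n = 50 / 0.20 = 250. This matches. No term for loss enters it.

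**Step 2: chance of reaching 50 at the ceiling.** Let X be the number of quit pairs, with X ~ Binomial(n, p).

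- n = 250, p = 0.20: mean 250 × 0.20 = 50; standard deviation √(250 × 0.20 × 0.80) = 6.3; 2.5th and 97.5th percentiles 38 and 63; P(X ≥ 50) = 0.525.
- n = 250, p = 0.22: mean 55; P(X ≥ 50) = 0.798.

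**Step 3: allow for loss before the TP3 sample.** Replace p by p × (1 − d), with n = 250.

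| Quit rate | Assumed loss d | p × (1 − d) | Expected pairs | P(X ≥ 50) |
|---|---|---|---|---|
| 20% | 0 | 0.200 | 50 | 0.525 |
| 20% | 5% | 0.190 | 47.5 | 0.368 |
| 20% | 10% | 0.180 | 45 | 0.227 |
| 20% | 20% | 0.160 | 40 | 0.054 |
| 22% | 0 | 0.220 | 55 | 0.798 |
| 22% | 10% | 0.198 | 49.5 | 0.494 |

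**Step 4: the lower planned size.** With n = 150 and p = 0.20 the mean is 150 × 0.20 = 30, and P(X ≥ 50) is about 0.0001. With p = 0.22 the mean is 33. For 150 recruits merely to be expected to yield 50 pairs, the quit rate would have to be 50 / 150 = 33%, a rate found nowhere in the protocol.

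**Step 5: nasal pairs.** A participant needs a baseline buccal sample to stay in the study but may omit the nasal samples at either visit. Provided the buccal sample is also taken at TP3, as scheduled, nasal quit pairs cannot exceed buccal quit pairs. The protocol gives no uptake figure, so no number can be attached.

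**The case against.** The strongest reply is that the study is exploratory. The protocol sets no significance level, power or effect size, and nothing in section 3.3 is conditional on having 50 pairs. With 40 or 45 pairs no analysis becomes invalid. This stands, and it limits the severity. It does not turn a mean into a minimum.

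Second, the 20% is approximate and describes current smokers generally, whereas participants must intend to quit within three months. Their rate may be higher, and the chance of reaching 50 is sensitive to it: 0.53 at 20%, 0.80 at 22%, and 0.97 at an assumed 25%, all without loss. So 53% is not a forecast; it is what the plan's own rate implies. The protocol states no higher rate for its participants.

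Third, the loss percentages are assumptions. The data behind the 20% are not shown, and if people who could not be reached were already counted as non-quitters, a further deduction partly counts loss twice. TP3 for a quitter is also arranged only after abstinence is reported, so loss among quitters may be small. This stands as a caution on the 45 and the 23%. It does not affect the result without loss.

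Some stronger readings are tempting, but the documents do not support them:

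- *The 250 is a miscalculation.* It is not: step 1 reproduces it. The fault lies in how the result is described.
- *The study plans to stop at 150 and will fall short.* Nothing says it will stop at 150 with a 20% quit rate. The range may describe recruiting until enough pairs exist, though that is not written either. The supportable point is that the two statements of size are not reconciled.
- *The protocol promises 50 nasal pairs.* Section 5.2.1 gives no nasal number, and nasal sampling is openly optional.

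**Conclusion.** The point holds as a misstatement of moderate severity. On the protocol's own rate, 250 recruits yield 50 quit pairs on average, with a 95% range of 38 to 63 and about a 53% chance of reaching 50 before any loss. At the 22% in section 1.2 the chance is about 80%, which is still not assurance. Loss before TP3 can only lower these figures. The lower planned size gives an expected 30.

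The calculation assumes that participants quit independently at one common rate and that this rate is the one stated. The figures with loss rest in addition on assumed losses.

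A reader might infer that the study is underpowered or must recruit more. The documents do not support that: there is no power claim to miss, and no analysis depends on reaching 50. What must change is the description of the number.

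**What to change.** In section 5.2.1, remove the claim that 50 is an ensured minimum and put in its place text such as:

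*With 250 recruits and a quit rate of about 20% we expect about 50 buccal quit pairs before loss to follow-up (95% range 38 to 63). Under an assumed 10% loss we expect about 45. With 150 recruits we expect about 30 before loss. Nasal quit pairs will be no more than the buccal pairs, because nasal sampling is optional.*

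Then reconcile the 150 to 250 in the Study Summary with the single ceiling in section 5.2.1, so that both places state the same planned size.

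The cost is protocol wording only. The stated figure becomes less favourable, but recruitment, visits and analyses are unchanged. A rule tying the end of recruitment to a count of banked pairs should not be added as part of this correction: it would be a new operating rule and could add up to 250 − 150 = 100 recruits compared with stopping at the lower planned size.

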### **5.2.2. Sampling technique**

We will recruit consecutive individuals attending the Greater Manchester LHC service or MFT-CURE service who meet the study's eligibility criteria. It is anticipated that recruitment will be completed over a 30-month period. Follow up will commence any time after the first telephone assessment and continue for a further period of 3 months after the last participant has been recruited.

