**STUDY SUMMARY**

Study Title	Discovering the molecular signatures of cancer PROMotion to INform prevention (PROMINENT): Smoking Cessation Study
Internal ref. no. (or short title)	PROMINENT: Smoking Cessation Study (Sponsor Reference Number: NHS002126)
Study Design	Observational study
Study Participants	Current smokers, aged ≥55 years old, no prior history of cancer
Planned Size of Sample (if applicable)	150 - 250
Follow up duration (if applicable)	Between 3 and 12 months after recruitment
Planned Study Period	3rd June 2024 – 31 st May 2027
Research Question/Aim(s)	Study the impact of smoking cessation on the molecular architecture of human buccal and nasal cells.

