**5.4.2. Timepoint 2 (TP2)**

Study participants will be contacted by a member of the research team to ascertain smoking status. This will be undertaken over the telephone and will involve the completion of a study questionnaire. It is anticipated that phone calls will be made every 3 months to ascertain smoking status. TP3 will be arranged if the participant has not smoked a cigarette for at least three consecutive months prior to the proposed date of TP3. If by 3-12 months after baseline a participant remains a current smoker (smoked within three months of the telephone assessment) they will then have TP3 arranged.

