## PROMINENT Smoking Cessation Study

**5.4.4. Timepoint 4 (TP4)**

Participants who attend TP3 who are classified as a former smoker will be invited to attend a further appointment 3 to 6 months after TP3 (TP4). Samples collected at TP4 include the following

- Buccal swab
- Mouthwash sample
- Breath carbon monoxide measurement
- Nasal swab (optional)
- Nasal brush (optional)
- Blood sample (optional) – 50mL volume maximum

Study questionnaires will be completed by the participant, at all timepoints, either at the study visit or over the telephone (with a member of the research team recording the participant's response to questions). This can be completed electronically (an electronic device will be available on site for this purpose) or on paper.

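### Sample follow-up closes 3 months after the last recruit, leaving late recruits little or no time to qualify as quitters and essentially none to give a TP4 sample

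*Protocol*

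**What the plan says.** Protocol 5.2.2 expects that "recruitment will be completed over a 30-month period" and that follow-up will "continue for a further period of 3 months after the last participant has been recruited". It also starts follow-up only after the first telephone assessment, and 5.4.2 anticipates those calls every 3 months.

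The rules that this window has to accommodate are:

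- **Entry (5.1.1, 5.1.2).** Participants need only intend a quit attempt within 3 months. The exclusion criteria admit people whose last cigarette was up to 2 weeks earlier, subject to the carbon monoxide criterion.
- **Quitter at TP3.** Section 5.4.3 requires "last cigarette over three months ago i.e. a last cigarette 3 months plus 1 day ago = former smoker". Section 3.3 defines the Quit Cohort as "stopped smoking for 3 months or more at the time of sample collection". Section 5.4.2 arranges a quitter's TP3 once the participant has "not smoked a cigarette for at least three consecutive months prior to the proposed date of TP3".
- **Everyone else (3.3).** Anyone who smoked within 3 months of sampling belongs to the Smoking Cohort.
- **TP4 (5.4.4).** Former smokers at TP3 are invited to one more sampling visit, 3 to 6 months later.
- **Overall duration (Study Summary).** "Between 3 and 12 months after recruitment".

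No section exempts late recruits or extends sampling for them. The 10-year follow-up in 6.9 is record review, not sampling.

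**The concern.** The last recruit has 3 months of follow-up. That roughly equals the abstinence needed to count as a quitter, so it leaves no room for the delay to the quit attempt that the entry criterion allows. It is about half the time to the earliest TP4. On the anticipated call schedule, the last recruit's first telephone assessment falls at about the moment follow-up closes.

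Three things are at stake:

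- **Cohort membership** depends partly on recruitment date. A late recruit who has been abstinent for 2 months and is sampled at closure is analysed as a smoker, which dilutes the quit-versus-smoke contrast behind the primary objectives.
- **The pair target.** The sample size in 5.2.1 reaches 50 quitter pairs with nothing to spare.
- **The quit rate** for the secondary objective on cessation effectiveness (2.1.2) is pulled down if people without a sufficient window count as non-quitters.

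**Working it through.** **The plan's own figure.** Section 5.2.1 wants at least 50 pairs at a quit rate of about 20%: 50 / 0.20 = 250. This reproduces the stated maximum exactly, with no allowance for dropout. With 250 recruits and a true rate of 20%, the binomial probability of at least 50 quitters is about 0.53 before any timing loss.

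**Set-up.** Let *c* be the months of follow-up after the last recruit (3 in section 5.2.2), *t* the months before the close of recruitment at which a person joins, and *D* the months from baseline to the last cigarette. Available follow-up is *c* + *t*. A quitter's TP3 needs *D* + 3 months (plus 1 day under 5.4.3). The earliest TP4 needs *D* + 6.

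**Assumptions.** Accrual is uniform over the 30 months in 5.2.2. *D* is 0, uniform on 0 to 3, or 3, the limit in the entry criterion. The protocol states neither the accrual pattern nor quit dates.

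**Formulas.** Share of quitters losing TP3 = mean of max(0, *D* + 3 − *c*) / 30. Share losing even the earliest TP4 = mean of max(0, *D* + 6 − *c*) / 30.

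**As planned (*c* = 3), out of 50 quitters:**

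| Quit date | TP3 loss | Quitter pairs | TP4 loss | Time for earliest TP4 |
|---|---|---|---|---|
| Day 0 | 0/30 = 0% | 50.0 | 3/30 = 10% | 45.0 |
| Uniform, months 0–3 | 1.5/30 = 5% | 47.5 | 4.5/30 = 15% | 42.5 |
| Month 3 | 3/30 = 10% | 45.0 | 6/30 = 20% | 40.0 |

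**The last 3 months of recruitment.** 250 / 30 = 8.33 recruits a month, so 25 people and 25 x 0.20 = 5 expected quitters. A quitter TP3 is possible for all, half or none of them (*D* = 0, uniform, 3). TP4 is possible for none who quit at or after baseline. A last cigarette up to 2 weeks before entry shifts this by at most 2 weeks.

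**Effect on the quit rate** if all 250 stay in the denominator: 47.5 / 250 = 19.0% instead of 20% (range 45 / 250 = 18.0% to 50 / 250 = 20.0%).

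**Closing 6 months after last recruitment (*c* = 6).** The TP3 loss is 0% in all three cases. The earliest-TP4 loss is 0%, 1.5/30 = 5% or 3/30 = 10%, which leaves 50.0, 47.5 or 45.0.

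**Does 6 months fit?** Thirty months from 3 June 2024, the start of the study period in the Study Summary, is 3 December 2026. From there to 31 May 2027 is 179 days, about 5.9 months. That is a maximum, because it takes recruitment to have opened on the first day of the study period.

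**Length of the schedule.** Earliest TP4: 3 + 3 = 6 months from baseline. Latest: 12 + 6 = 18 months. The summary's range stops at 12.

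**The case against.** A reader might infer that late recruits cannot be quitters at all. The documents do not support that. Sections 3.3 and 5.4.2 accept exactly 3 months, and only 5.4.3 asks for a day more. The entry criteria allow a last cigarette up to 2 weeks before enrolment, so even the last recruit is not always ruled out. Someone recruited *t* months before the close can still qualify by quitting within about *t* months. Section 1.2 describes treatment starting on the day of assessment, so quits near baseline are plausible, and with a baseline-day quit the TP3 loss is about zero.

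A reader might also count everyone with under 12 or 18 months of follow-up as lost. Those are outer limits of the visit windows, not required follow-up.

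The further objections have some force:

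- **TP4 is peripheral.** It is by invitation, has no target number, and is not named in the laboratory comparison in 3.3, which sets baseline against TP3. The TP4 loss therefore leaves the main comparison and the 50-pair target untouched.
- **The closing date is not the only cause of misclassification.** Section 5.4.2 lets TP3 be arranged from month 3 for anyone who smoked in the previous 3 months, so a recent quitter recruited at any time could be labelled a smoker. For late recruits, however, closure removes the option of waiting.
- **Quit-rate denominators may be in a statistical analysis plan.** That is possible. But the two-way cohort split and the closing date are fixed in this protocol.

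What remains is that the closing date does not fit the protocol's own visit rules.

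**Conclusion.** The point holds as a conflict of timing with a modest but systematic loss. Follow-up of 3 months after the last recruit cannot accommodate the permitted quit delay, the abstinence needed at TP3 and the interval to TP4. The expected cost is 0 to 5 of 50 quitter pairs (2.5 if quits are spread evenly over months 0 to 3) and 5 to 10 of 50 possible TP4 samples (7.5 on the same assumption). These figures rest on uniform accrual over 30 months, a 20% quit rate, 250 recruits and no dropout. Slower early or faster late accrual would make the losses larger.

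The study is exploratory and a few lost pairs would not undermine it. The loss still falls on the group that the study is built around, against a target with no margin, and it sends some abstinent people into the comparison cohort. It should be corrected.

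**What to change.** 1. Reconcile 5.2.2 with 3.3, 5.1.1, 5.4.2, 5.4.3 and 5.4.4, and state one abstinence threshold in place of the two now in use (3 months or more, and 3 months plus 1 day).
2. Replace the 3-month closure in 5.2.2 with a last-sample date as late as the study period in the Study Summary allows, ideally about 6 months after last recruitment.
3. In 3.3, analyse participants who are abstinent at sampling but cannot yet have 3 months' abstinence separately from the Smoking Cohort.
4. Compute quit rates only in participants with enough follow-up to qualify.
5. Correct the follow-up duration in the Study Summary to include TP4, that is, up to 18 months.

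Items 1, 3, 4 and 5 are wording. Item 2 means visits running up to about 3 months longer, which leaves less time for laboratory work before the study ends (5.6 ties the end of study to completed analysis). The full 6 months fits only roughly, at 5.9 months at most, so items 3 and 4 are needed whatever date is chosen.
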